7.4 Blinding

The study will be participant and laboratory blinded, i.e., while staff involved in study delivery will be aware of what vaccine schedule the participant is receiving, the participant themselves will remain blinded to which vaccine they receive. The "short" or "long" prime-boost interval allocation will be blinded to participant, where possible. This will be achieved in cohort 1, but in cohort 2, the pertussis-containing vaccine in the "long" prime-boost interval arm cannot be given at a COVID-19 vaccine visit (if after 32 weeks' gestation), and thus the whole cohort will be not blinded to "short" or "long" prime-boost intervals. During vaccination, the blind will be maintained by applying masking tape over the vaccine syringe. Laboratory staff will be blinded to both the randomised vaccines and the prime-boost intervals.

The timing of final unblinding of all trial participants will be after the creation of a locked analysis data set.

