Although there is no minimum gestational age for receipt of a COVID-19 vaccine in pregnancy, it is recognised that COVID-19 has more serious complications in later pregnancy (Knight et al. 2020) and so maximal protection should be provided by the third trimester. Additionally, women may prefer to avoid vaccination in the first trimester (when fetal development is greatest). The ideal window for vaccination may therefore be between 13 and 27+6 weeks gestation, although it is recognised that in a vaccine programme some women may present later than this and still require protection against COVID-19. A maximal gestational age of 36 weeks for a second dose of vaccine is therefore proposed. A trial primary endpoint of delivery anti-S antibody concentrations has been chosen as a “fixed point” to correspond with the primary objective of maximal protection in the 3rd trimester of pregnancy.

Pertussis-containing vaccine in pregnancy.

A single dose of a pertussis containing vaccine (dTaP/IPV) is routinely recommended in each pregnancy. This can be offered from 16 weeks' gestation, although in practice is often given after the routine anomaly scan at 20 weeks' gestation. It is ideally administered by 32 weeks' gestation. Women may find it helpful to receive this vaccine as part of this trial, so it is therefore incorporated into the schedules.

Study design.

In order to incorporate the considerations around intervals between doses, gestational age at vaccination and achieving maximal protection against COVID-19 in the third trimester, as well as offering the opportunity to receive the pertussis-containing vaccine, the trial will need to include several schedules (cohorts, see below). The inclusion of the pertussis-containing vaccine will additionally allow convenient “blinding” of the schedule of COVID-19 vaccines received.

Cohorts 1 and 2 will be main study cohorts on which the sample size calculation is based on.

Cohorts 3 and 4 will be the sub-study cohorts.

Table 1. Cohort 1.

Recruitment window (wk)	Total n=200 for each vaccine for cohort 1 + cohort 2	Day 0	Short 4-6 wk	Long 8-12 wk*
13 0/7 – 23 6/7		Vaccine A	dTaP/IPV	Vaccine A
		Vaccine A	Vaccine A	dTaP/IPV
		Vaccine B	dTaP/IPV	Vaccine B
		Vaccine B	Vaccine B	dTaP/IPV
		Vaccine C	dTaP/IPV	Vaccine C
		Vaccine C	Vaccine C	dTaP/IPV

* “Long” dose must be given by 32 weeks’ gestation i.e. if recruited between 21 to 23+6 weeks gestational age, long dose should be given 8 weeks later.

Table 2. Cohort 2.

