 - **Vaccination with COVID-19 vaccine if randomised to the short interval boost or dTaP/IPV if randomised to the long boost arm and has not previously received pertussis vaccine.**
 - Observation period post-vaccination for 20 minutes
- **Cohort 2.**
 - Vital signs pre-vaccination

- **Vaccination with COVID-19 vaccine if randomised to the short interval boost or no vaccine or dTaP/IPV if randomised to the long interval boost arm and has not previously received pertussis vaccine. If dTaP/IPV vaccination is requested, it should be given by 32 weeks' gestation and with an interval of at least 1 week before / after receipt of COVID-19 vaccine.**
- Observation period post-vaccination for 20 minutes
- **No vaccination for cohort 3 (28 0/7 – 34 0/7 gestational weeks at recruitment) and cohort 4 (COVID-19 vaccine received pre-pregnancy / first trimester (0 0/7 – 12 6/7 gestational weeks)).**

Study visit 4 (Maternal) Cohort 1 and 2 only

Day 56-84 following the first vaccination (or 28-42 days post-short interval boost dose) at the participating institution.

- SAE / AESI / MAAE check
- Concomitant medication check
- Diary card review if applicable
- Targeted physical examination if indicated
- Immunogenicity blood samples will be collected

- **Cohort 1.**
 - Vital signs pre-vaccination
 - **Vaccination with COVID-19 vaccine if randomised to the long interval boost or dTaP if randomised to the short interval boost arm and has not previously received the pertussis vaccine**
 - Observation period post-vaccination for 20 minutes
 - eDiary review

- **Cohort 2.**
 - Vital signs pre-vaccination
 - **Vaccination with COVID-19 vaccine if randomised to the long interval boost or no vaccine or dTaP/IPV if randomised to the short interval boost arm and has not previously received pertussis vaccine. If dTaP/IPV vaccination is requested, it should be given by 32 weeks' gestation and with an interval of at least 1 week before / after receipt of COVID-19 vaccine.**
 - Observation period post-vaccination for 20 minutes
 - eDiary review

- **No visit 4 for cohort 3 (28 0/7 – 34 0/7 gestational weeks at recruitment) and cohort 4 (COVID-19 vaccine received pre-pregnancy / first trimester (0 0/7 – 12 6/7 gestational weeks)).**

Study visit 5 (Maternal) Cohort 1 and 2 only

Day 84-112 following the first vaccination (or 28-42 days post-long boost dose) at the participating institution / participant home.

- SAE / AESI / MAAE check
- Concomitant medication check

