16.3 Appendix 4 – Schedule of Events / Procedure

Cohort 1 and 2 Visit Schedule - Pregnant women enrolled between 13 0/7 - 27 6/7 gestational weeks

	PRENATAL						DELIVERY	POSTNATAL				
	Screening + V1	V2	V3	V4 ^b	V5 ^b	V6 ^c	V7	V8 ^e	V9 ^f	V10	V11	V12
Study timeline	D0	D14	D28-42	D56-84	D84-112	D112 - 140	Delivery	Delivery up to 7 days (where possible)	Delivery +14 days (where possible)	Delivery +28-42 days OR 70-84 days	Delivery +182 days (+/- 14 days)	Delivery +364 days (+/- 14 days)
Study window	D0	Day 10-21 post V1 (phone)	Day 28-42 post V1	Day 56-84 post V1	Day 28-42 post V3	Day 56-84 post second COVID vaccine	N/A	0 - 7 days post delivery	Day 12-16 post delivery (phone)	Day 28-42 OR 70-84 post delivery	Day 168-196 post delivery (phone)	Day 349-379 post delivery
Informed consent	X											
Screening bloods - maternal (HIV, Hep B, Syphilis) from routine prenatal visits	X (routine)											
Ultrasound dating and anomaly scan from routine prenatal visit	X (routine)											
Medical History	X											
Physical examination - maternal	X		(X)	(X)	(X)	(X)	(X)			(X)		
Vital signs, height and weight	X		X	X								
Vaccination	X		X ^a	X ^a								
COVID-19 immunogenicity bloods - maternal	X		X	X	X	X	X			X		X
eDiary review		X	X	X	X	X						
SAE/AES/Medically attended AE check		X	X	X	X	X		X	X	X	X	X
Concomitant medication check	X	X	X	X	X	X		X	X	X	X	X
Physical examination - infant							X					X
COVID-19 immunogenicity bloods - infant										X ^d		
Neurodevelopmental assessment (Ages & Stages questionnaire) - infant												X
Cord blood sample (selected sites)							X					
Colostrum / Breast milk sample (selected sites)								X	X			

^a For cohort 1, this will be a COVID-19 vaccine or pertussis-containing vaccine depending on randomisation to long or short course. A pertussis-containing vaccine may also be offered in cohort 2, 3, 4.
^b Participants will either have blood sampling for Neutralising Antibody, ELISpot, Intracellular Cytokine Staining assays at V4 or V5 depending on whether they are on the short course or long course.
^c This visit will take place if the window starts before their due date.
^d Infant is randomised at V9 to blood sampling at 4-6 weeks or 10-12 weeks after birth except cohort 3 (cohort 3 will have infant and maternal blood samples taken at 28-42 days post-delivery).
^e V8 only for breast milk sub-study sites or Cohort 3
^f V9 is a telephone call review except for breast milk sub-study sites (in brackets) - as required

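### Interval blinding is claimed for the whole of cohort 1, but the masking pertussis injection is withheld from women who have already had pertussis vaccine

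*Protocol*

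**What the plan says.** - **The claim.** Section 7.4 states that the "prime-boost interval allocation will be blinded to participant, where possible". Its next sentence begins "This will be achieved in cohort 1, but in cohort 2, the pertussis-containing vaccine in the" and explains why cohort 2 is left unblinded to interval. No exception is made within cohort 1.
- **The device.** Section 2 (Study design) says "The inclusion of the pertussis-containing vaccine will additionally allow convenient" masking of the COVID-19 schedule. Table 1 shows an injection for every cohort 1 woman at both the short and the long time point. The footnote to the visit schedule in Appendix 4 (Section 16.3) is equally unconditional: "For cohort 1, this will be a COVID-19 vaccine or pertussis-containing vaccine depending on randomisation to long or short course".
- **The condition.** Section 7 makes the masking injection conditional in both arms. Visit 3 gives "dTaP/IPV if randomised to the long boost arm and has not previously received pertussis vaccine". Visit 4 gives "dTaP if randomised to the short interval boost arm and has not previously received the pertussis vaccine". Nothing is given in its place.
- **Routine use.** On pertussis vaccine in pregnancy, Section 2 says "This can be offered from 16 weeks' gestation, although in practice is often given after the routine anomaly scan at 20 weeks' gestation". Prior receipt is not among the exclusions in Section 6.2, and Section 9.6 has women asked about it.
- **A weaker statement elsewhere.** The data protection assessment (Appendix 7) says only that most participants will be blinded to the interval.

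**The concern.** The blind to interval works only if each woman has an injection at both visit 3 and visit 4 and cannot tell which was the COVID-19 vaccine. Masking tape on the syringe hides what is injected. It cannot hide that nothing was injected, or that only one product remained possible.

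Solicited and unsolicited adverse events are primary outcomes (Section 3.4), are self-reported by eDiary (Sections 8.11 and 11.1), and are presented by schedule received (Section 10.3.3). Cohort 1 is the only cohort for which 7.4 says interval blinding will be achieved. If some of its women know what dose 2 is when they fill in the diary, a reader of the results would credit those data with a safeguard they did not have. Nothing in the protocol says that the number of such women will be reported.

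**Working it through.** The protocol gives no figure to reproduce here. The check sets the passages side by side and then counts days.

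**Step 1: what each cohort 1 woman receives under the Section 7 instructions**

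| Pertussis vaccine outside the trial | Arm | Visit 3 | Visit 4 | When she can infer her interval |
|---|---|---|---|---|
| None | Short | COVID-19 | Pertussis | Masked |
| None | Long | Pertussis | COVID-19 | Masked |
| Before visit 3 | Short | COVID-19 | Nothing | Visit 3: the injection can only be COVID-19 |
| Before visit 3 | Long | Nothing | COVID-19 | Visit 3: no injection |
| Between visits 3 and 4 | Short | COVID-19 | Nothing | Visit 4: no injection |

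The last case has no long-arm counterpart, because the trial itself gave that woman the pertussis vaccine at visit 3. The table assumes that a woman knows the two products used at these visits and her own pertussis history.

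**Step 2: which diaries are open when she can infer it**

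The solicited window is the vaccination day plus 6 days. The unsolicited window is the vaccination day plus 29 days (Section 3.4).

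- *Dose 1, both arms.* Given on Day 0; visit 3 is Day 28 to 42. The solicited window closed on Day 6. The unsolicited window ends on Day 29, so at most Days 28 and 29 overlap. Dose 1 is effectively untouched.
- *Dose 2, vaccinated before visit 3.* In the short arm she knows at the injection itself. In the long arm she has known since visit 3, at least 56 − 42 = 14 days before dose 2. The whole dose-2 diary is completed with that knowledge in both arms.
- *Dose 2, short arm, vaccinated between visits 3 and 4.* Section 7 puts visit 4 at 28 to 42 days after the short-interval boost, when the 7-day diary is closed and the 30-day window nearly so. If only the window of Day 56 to 84 after the first dose is applied, with visit 3 on Day 42, the gap is 14 days. That is still beyond the solicited window, although the unsolicited window would be open.

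The status that matters for dose-2 solicited reactions is therefore pertussis status at visit 3, in both arms.

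**Step 3: is prior receipt foreseeable by visit 3?**

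- Cohort 1 enrolment window, 13 0/7 to 23 6/7: 11 weeks × 7 = 77 days.
- Enrolment days at or after 16 0/7: 8 × 7 = 56, and 56/77 = 73%.
- Enrolment days at or after 20 0/7: 4 × 7 = 28, and 28/77 = 36%.
- Earliest gestation at visit 3: 13 0/7 + 28 days = 17 0/7. Every cohort 1 woman has passed 16 weeks by then.

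The percentages are shares of calendar days in the window, not of participants. Being within the offer period is not the same as having been vaccinated.

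**The case against.** The strongest reply is that this is a one-clause mismatch with little consequence. Most of its parts have force.

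- *Incomplete blinding is already admitted.* Section 7.4 says where possible, Appendix 7 says most participants, and openly unblinded cohort 2 is pooled with cohort 1 for the primary analysis (Section 10.3.2). This shows that the design tolerates some unblinded women. It does not rescue a sentence that claims achievement in cohort 1 without exception.
- *The tested endpoint is safe.* Anti-spike IgG at delivery is measured by laboratory staff blinded to vaccine and interval. This stands. A reader might infer that the antibody comparison is compromised; by this route it is not.
- *Reactogenicity is descriptive and covers all vaccinated women.* Section 10.3.3 plans counts and percentages, with no cohort 1 set and no short-versus-long test. This stands and limits the consequence.
- *The unblinding is symmetric.* A woman vaccinated before visit 3 knows in either arm that dose 2 is COVID-19 vaccine, and the brand stays masked. This stands. A reader might infer a bias between short and long arms, but the protocol shows no mechanism for one.
- *The number affected may be small.* Section 2 offers pertussis vaccine within the trial because women may find that convenient, which could lead some to wait. The documents neither confirm nor exclude this.
- *An earlier pregnancy should not count.* Section 9.6 asks about vaccination in this pregnancy and Section 2 describes a dose in each pregnancy, so current pregnancy is the likelier meaning of previously. The visit 3 and 4 text does not say so, and the ambiguity needs settling.

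**Conclusion.** The point holds in limited form. As written, the design does not have the property that 7.4 states for cohort 1. Women vaccinated against pertussis before visit 3 can infer their interval at visit 3 in both arms, and what is exposed is their self-reported dose-2 reactogenicity.

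The size is unknown. If, purely as an assumption, 10% to 40% of cohort 1 had received the vaccine before visit 3, the same 10% to 40% would be unmasked before completing the dose-2 diary. The protocol supports neither end of that range. A reader might take the 73% or 36% above as the share of women unblinded, but those figures describe enrolment days only.

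The conclusion rests on Section 7 being followed as written, on no other masking injection being used, and on women being able to reason from what they are given. It should be corrected because the claim is categorical, the case is foreseeable and the remedy is cheap. It does not threaten the primary antibody analysis.

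**What to change.** 1. In Section 7.4, limit the cohort 1 claim to women eligible for the pertussis-containing vaccine at their masking visit, and state that the others may infer their interval.
2. Reconcile Section 7.4, the visit 3 and 4 instructions in Section 7, Table 1 and the pertussis paragraph in Section 2, the Appendix 4 footnote and Appendix 7. Include whether previously refers to this pregnancy. Which clinical rule applies is for the investigators; the passages must agree.
3. Record pertussis status for this pregnancy at visit 1 and again at visit 3 before any injection, in the same way in both arms. Report by arm how many cohort 1 women were interval-blinded.
4. Keep the Section 10.3.3 analysis of all vaccinated women as the main one. Add a supplementary table of dose-2 solicited and unsolicited events by schedule, split by pertussis status at visit 3.

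Do not split on a flag set at the arm-specific masking visit. That visit is at 4 to 6 weeks in the long arm and 8 to 12 weeks in the short arm. Short-arm women would have longer to be vaccinated elsewhere, so the flag would select differently by arm.

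The cost is protocol wording, one status check at visit 3, one derived variable and one extra table based on smaller numbers. Most of the history is already collected under Sections 7.6 and 9.6.

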3.5 Secondary endpoints/outcomes

Maternal

- Pregnancy outcomes from Visit 1 up to 6 weeks after delivery. These include live birth with congenital anomalies, miscarriage, fetal death/still birth (antepartum or intrapartum), mode of delivery, elective/therapeutic termination.
- Occurrence of serious adverse events (SAEs), AEs leading to study withdrawal, and MAAEs from Visit 1 (Day 0) up to 6 weeks / 6 months after delivery

- AEFI from Visit 1 up to 6 weeks after delivery. These include but are not limited to maternal death, hypertensive disorders of pregnancy (gestational hypertension, pre-eclampsia, pre-eclampsia with severe features including eclampsia), antenatal bleeding (morbidly adherent placenta, placental abruption, caesarean scar pregnancy, uterine rupture), postpartum haemorrhage, fetal growth restriction, gestational diabetes mellitus, non-reassuring fetal status, pathways to preterm birth (premature preterm rupture of membranes, preterm labour, iatrogenic preterm birth), chorioamnionitis, oligohydramnios, polyhydramnios, gestational liver disease (intrahepatic cholestasis of pregnancy, acute fatty liver of pregnancy), maternal sepsis.
- SARS-COV-2 IgG-specific antibody concentrations, (and neutralizing antibody titres and cellular immune responses in subsets) measured on blood samples collected from vaccinated maternal subjects at Day 0 (before vaccination), Day 28-42, Day 56-84, Day 84-112, Day 112-140, at delivery, between 4 weeks and 12 weeks, and at 12 months after delivery

Infant

- From birth through 6 weeks after birth, occurrences of SAEs, AEs leading to study withdrawal, and MAAEs
- Occurrence of neonatal AEs of special interest (up to 6 weeks after birth). These include but are not limited to small for gestational age, low birth weight including very low birth weight, neonatal encephalopathy, congenital microcephaly (postnatally or prenatally diagnosed), congenital anomalies (major external structural defects, internal structural defects, functional defects), neonatal death (in a preterm live birth or in a term live birth), neonatal infections (blood stream infections, meningitis, respiratory infection), respiratory distress in the neonate, preterm birth, failure to thrive, large for gestational age, macrosomia
- Developmental status at 12 months of age

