7.11.2 Blood sampling (refer to the Laboratory Analysis Plan)

- Blood samples will be obtained by venepuncture by appropriately trained members of the research team. If it is not possible to obtain a venous sample from the infants, capillary blood sampling is acceptable although venous blood samples are preferable.
- Samples should be labelled with the participant number (prefixed with Preg-CoV), date of sampling and study visit number.
- Cord blood volumes. The required volume of cord blood is 30mls
- Maternal blood volumes. Refer to lab manual.
- Infant blood volumes. The required volume of infant blood is up to 5ml (no more than 1% of circulating blood volume)

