COVID-19 immunogenicity bloods - maternal	X Nexelis Anti-spike IgG	X Nexelis Anti-spike IgG	X Nexelis Anti-spike IgG	X Nexelis Anti-spike IgG	X Nexelis Anti-spike IgG	X Nexelis Anti-spike IgG	X Nexelis Anti-spike IgG			X Nexelis Anti-spike IgG		X Nexelis Anti-spike IgG	
	PHE Anti-nucleocapsid IgG ADCC	PHE Neutralising Abs ADCC	PHE Neutralising Abs ADCC	PHE Neutralising Abs ADCC	PHE Neutralising Abs ADCC	PHE Anti-nucleocapsid IgG Neutralising Abs ADCC	PHE Anti-nucleocapsid IgG Neutralising Abs ADCC					PHE Anti-nucleocapsid IgG ADCC	
	IMMUNOTEC ELISpot & ICS (7 sites)	IMMUNOTEC ELISpot & ICS (7 sites)	IMMUNOTEC ELISpot & ICS (7 sites)	IMMUNOTEC ELISpot & ICS (7 sites)	IMMUNOTEC ELISpot & ICS (7 sites)	SGUL Lab ELISpot & ICS (2 sites)	SGUL Lab ELISpot & ICS (2 sites)					IMMUNOTEC ELISpot & ICS (7 sites)	
Cord blood sample (at selected sites)						X Nexelis Anti-spike IgG	X Nexelis Anti-spike IgG						
Colostrum / Breast milk sample (at selected sites)							X SGUL Lab Anti-spike IgG ELISpot + ICS (2 sites)	X SGUL Lab Anti-spike IgG ELISpot + ICS (2 sites)	X SGUL Lab Anti-spike IgG ELISpot + ICS (2 sites)				
COVID-19 immunogenicity bloods - infant										X Nexelis Anti-spike IgG			
	Maternal: Up to 50mls (20mls red, 30mls green/ LIHep)	Maternal: Up to 50mls (20mls red, 30mls green/ LIHep)	Maternal: Up to 50mls (20mls red, 30mls green/ LIHep)	Maternal: Up to 50mls (20mls red, 30mls green/ LIHep)	Maternal: Up to 50mls (20mls red, 30mls green/ LIHep)	Maternal: Up to 50mls (20mls red, 30mls green/ LIHep)	Maternal: Up to 50mls (20mls red, 30mls green/ LIHep)	Maternal: Up to 50mls (20mls red, 30mls green/ LIHep)	Breast milk: 2-5mls	Maternal: Up to 20mls (20mls red) Infant: up to 5mls		Maternal: Up to 50mls (20mls red, 30mls green/ LIHep)	

^aThis will either be a COVID vaccine or pertussis-containing vaccine for cohort 1 depending on randomisation to long or short course. A pertussis-containing vaccine may also be offered in cohort 2, 3, 4.

^bParticipants will either have Neutralising Abs, ELISpot, intracellular Cytokine Staining assays at V4 or V5 depending on whether they are in the short course or long course.

^cThis visit will take place if the window starts before their due date.

^dInfant is randomised at V9 to blood sampling at 4-6 weeks or 10-12 weeks after birth except cohort 3. Cohort 3 will have infant and maternal blood samples taken at 28-42 days post-delivery.

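### Laboratory blinding to the prime-boost interval (7.4) conflicts with arm-dependent V4/V5 sampling and visit-numbered tubes for the neutralising antibody, ELISpot and ICS assays in cohorts 1 and 2

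*Protocol*

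**What the plan says.** Section 7.4 makes the study blind to participants and to the laboratory, while staff delivering the study know the schedule. It names one exception: cohort 2 participants are not blinded to the interval. The sentence on laboratories carries no exception: "Laboratory staff will be blinded to both the randomised vaccines and the prime-boost intervals".

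Section 7.11.2 sets the tube label: "Samples should be labelled with the participant number (prefixed with Preg-CoV), date of sampling and study visit number".

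Appendix 4 (section 16.3), cohort 1 and 2 visit schedule, footnote b, says that women have blood sampling for neutralising antibody, ELISpot and ICS "assays at V4 or V5 depending on whether they are on the short course or long course". The laboratory sampling schedule for the same cohorts repeats the rule: "at V4 or V5 depending on whether they are in the short course or long course".

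Section 7 shows which visit belongs to which arm. V4 is "Day 56-84 following the first vaccination (or 28-42 days post-short interval boost dose) at the participating institution". V5 is "Day 84-112 following the first vaccination (or 28-42 days post-long boost dose) at the participating institution / participant home".

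Section 3.5 limits the reach of these assays. They are secondary endpoints, described with the words "and neutralizing antibody titres and cellular immune responses in subsets".

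**The concern.** Short versus long interval is the trial's primary contrast. Delivery staff know the interval, and cohort 2 participants are not blinded to it. In cohort 2 the laboratory blind is therefore the only blinding to interval that section 7.4 promises.

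The assays affected bear on a question that the protocol itself raises. Section 2 says that longer intervals may improve antibody responses at the expense of cellular responses, and that this balance needs study in pregnant women. ELISpot and ICS are the cellular read-outs. Staff who know the arm may also hold an expectation about the result. Wherever a reading or a decision to repeat a test involves judgement, that expectation can enter the data.

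There is also a conditional route to the primary result. Section 10.3.2 says that if 20% of the primary endpoint data are censored, an alternative primary outcome such as live neutralising antibody will be considered. Neutralising antibody is one of the assays affected.

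**Working it through.** No power or sample-size figure is involved. The check sets the protocol's rules side by side.

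**1. Does the V4/V5 rule follow the randomised interval?** Inputs are the boost windows in Tables 1 and 2 of section 2 (short 4-6 weeks, long 8-12 weeks) and the visit windows in section 7.

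- Short arm: boost at D28-42. Adding 28-42 days gives D(28+28) to D(42+42) = D56-84, which is the V4 window.
- Long arm: boost at D56-84, which is V4 itself. Adding 28-42 days gives D(56+28) to D(84+42) = D84-126, which contains the V5 window of D84-112.

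The sample taken 28-42 days after the boost is thus V4 in the short arm and V5 in the long arm. The mapping is one-to-one.

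One side observation: the study-window row of the cohort 1 and 2 schedule places V5 at 28-42 days after V3. That adds up to D56-84 and not the D84-112 in the row above it. The point here does not depend on this, because it rests on the visit number.

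**2. What does the laboratory see?**

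| Item | Rule | Source |
|---|---|---|
| Assay requested | Neutralising antibody, ELISpot, ICS at V4 or V5 by course | Appendix 4, footnote b, both schedules |
| Tube label | Participant number, date, visit number | 7.11.2 |
| Link to other samples | Couriered samples carry the participant identification number | Appendix 7, data flow |
| Recoding of visit number | None described | 7.4, 7.11, Appendix 4 |

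The assay request and the visit number together give the interval. The key to reading them is printed in the laboratory sampling schedule itself.

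**3. How far does the knowledge travel?** It travels through the participant number to other samples handled by the same laboratory.

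- *Neutralising antibody.* The schedule lists this assay under one laboratory, both antenatally and at delivery, so the link to the delivery sample is clear.
- *ELISpot and ICS.* The antenatal tests are listed under one laboratory (7 sites) and the delivery tests under another (2 sites), so the link to delivery is not established.
- *Anti-spike IgG.* This is listed under a separate laboratory at each maternal blood visit, including V4 and V5, and footnote b does not name it. Samples from both arms arrive at both visits, so the request reveals nothing.

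**4. Who is exposed?** Every woman in cohorts 1 and 2 whose post-boost sample goes to one of these assays. The protocol does not size the subsets, so no count can be given. ELISpot and ICS before delivery are listed for 7 of the approximately 15 sites in section 5.

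**The case against.** The strongest reply is that sample handling is delegated. Sections 7.11.1 and 7.11.2 refer to a Laboratory Analysis Plan, and 7.11.2 also cites a laboratory manual; neither is shown. Either could require aliquots to be recoded before assay staff see them. Section 7.11.1 says that samples sent elsewhere for exploratory tests remain anonymised. This lowers the certainty that the blind fails in practice. It does not remove the conflict, because the protocol fixes a label with the visit number and describes no masking step. Anonymising or pseudonymising a sample hides who the woman is, not which visit it came from.

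A second reply is that the neutralising antibody laboratory may receive V4 and V5 serum from both arms, since ADCC is listed beside neutralising antibody and footnote b does not restrict it. The laboratory table is broken in the text at hand, so shipment by visit cannot be read firmly. Even then, a neutralising request on only one of the two tubes would disclose the arm.

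A third reply stands in full: no bias is shown. The protocol says nothing on how much judgement these assays involve, and neither the size nor the direction of any effect can be derived from it.

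A reader might infer that all the laboratories are unblinded, that every woman's interval is revealed, or that the primary comparison is compromised. The documents support none of these. The primary anti-spike IgG assay is listed at a separate laboratory and is untouched by footnote b; the affected assays are run in subsets; and nothing has the other laboratories passing allocation to the anti-spike IgG laboratory.

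**Conclusion.** The point holds in limited form. The unqualified statement in 7.4 cannot be reconciled with footnote b and 7.11.2 for the laboratories running neutralising antibody, ELISpot and ICS in cohorts 1 and 2. For women sampled for these assays the disclosure is one-to-one with the randomised interval. The knowledge can extend to the delivery neutralising antibody result.

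This affects the credibility of secondary results on the short-versus-long contrast, which would be reported as laboratory-blinded when the protocol's own rules reveal the arm. It does not affect the planned primary analysis of anti-spike IgG at delivery. It would matter there only if neutralising antibody were adopted as the alternative primary outcome under 10.3.2.

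The conclusion assumes that assay staff see the label prescribed in 7.11.2 and know the schedule printed in Appendix 4. If the Laboratory Analysis Plan already recodes these samples, the remaining task is to say so in the protocol. The change should be made, but it is not critical to the trial's main result.

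**What to change.** **Preferred.** Amend 7.11.2 so that samples for neutralising antibody, ELISpot and ICS reach the assay laboratories under a code specific to the sample, without visit number or date. Hold the link to participant and visit centrally. The date has to go as well, because with the participant number it would allow the visit to be reconstructed. Run V4 and V5 samples in mixed batches where the assay allows. The cost is a label template, text in the laboratory manual, a sentence in 7.11.2 and upkeep of the code link. No additional samples are needed.

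**Otherwise.** Restrict the sentence in 7.4 so that it does not claim blinding to interval for the neutralising antibody, ELISpot and ICS laboratories, and describe those secondary results as not laboratory-blinded to interval when they are reported. This costs one sentence. It makes the description accurate but does not protect the results. If it is chosen, the protocol should also acknowledge the consequence for neutralising antibody as a possible alternative primary outcome in 10.3.2.
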